5.8.1 Females

Females of child-bearing potential must agree to use highly effective methods of contraception from baseline to approximately 30 days (one menstrual cycle) after the last dose of study drug. Highly effective methods are:

- combined (estrogen and progestogen containing) hormonal contraception associated with inhibition of ovulation administered by oral or intravaginal route.
- oral, injectable or implantable progestogen-only hormonal contraception associated with inhibition of ovulation.
- intrauterine device.
- intrauterine hormone-releasing system.
- bilateral tubal occlusion.
- bilaterally orchiectomized or vasectomized partner, provided that partner is the sole sexual partner of the subject, and in the case of a vasectomized partner has received medical assessment of the surgical success.
- true sexual abstinence, where this is in line with the usual lifestyle of the subject.

Periodic (calendar, ovulation, symptothermal or post-ovulation) abstinence and withdrawal are not acceptable methods of contraception.

Caution with co-administration of REN001 and hormonal contraceptives is advised due to the potential for drug-drug interaction ([Section 1.4](#)). In addition to highly effective hormonal contraception, WOCBP at risk of pregnancy are advised to also use an additional effective non hormonal method of contraception. Effective methods are male condom, female condom, cervical cap, diaphragm, contraceptive sponge.

Females are considered to be of non-child-bearing potential if they fulfil at least one of the following criteria:

- Post-menopausal, defined as 45 years or older and amenorrhoeic for at least 1 year PLUS have a serum follicle stimulating hormone (FSH) level within the laboratory's reference range for postmenopausal women, at screening or baseline visit.
- Have undergone a documented hysterectomy and/or bilateral oophorectomy.

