6.1.4.1 Screening Visit

- Obtain written informed consent. Subjects should be given adequate time to think about whether they want to participate and to ask questions. The Investigator (or an appropriate delegate at the site) will obtain written consent from each subject prior to commencing any specific study related activities or assessments.
- Subject Demography.
- Complete Medical History (including prescription and non-prescription drugs/treatment, non-drug treatments, topical products, vitamins and dietary

supplements taken in the last 4 weeks, alcohol, drugs of abuse and tobacco use. (See [Table 1](#) for prohibited medication and washout times).

- Review of ongoing concomitant medications and non-drug treatments. If subject is on any prohibited medications ([Table 1](#)), a washout period will be required, and the baseline visit should be scheduled after the washout period.
- Full physical examination (including weight and height).
- ECG.
- Vital signs (including temperature).
- Urinalysis and drugs of abuse testing.
- Blood samples for:
 - Haematology and biochemistry (including HbA1c, HIV/Hepatitis B/C serology)
 - Serum pregnancy test (WOCBP)
 - Serum FSH testing for all females (≥ 45 years)
- Eye examination (may be completed between Screening and Baseline visits).
- For subjects <25 years old (only) a wrist radiograph will be required to confirm bone growth plate closure.
- Optional DXA Scan (in those countries and sites where this is permitted). It should be scheduled as close as possible to the baseline visit, however if this is not feasible, then it must be performed within the 4 weeks after the baseline visit. Subjects must be checked against the Additional Criteria for Sites with approvals for DXA Scans ([Section 4.4](#)). All WOCBP must have a negative pregnancy test prior to the scan. All female subjects, regardless of child-bearing potential, must have an FSH test. Details of how the DXA scan will be performed can be found in the DXA Manual.
- 12MWT. Subjects must be able to walk at least 100m in the screening 12MWT and the limitations in walk test must be primarily due to the energy deficit and not due to ataxia or any other condition.
- Provide a urine collection cup and instructions for collecting a second morning void for next study visit. This is provided in case the subject has their second morning void before attending the study centre at their next study visit.

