- Menopausal status: males, pre-menopausal females or post-menopausal females. Post-menopausal females have a screening FSH value ≥ 23.0 IU/L and with either a date of last menstrual period > 1 year ago from date of first dose or a confirmed clinical history of sterility. Female subjects whose last menstrual period was > 1 year ago but do not have a screening FSH value will also be assumed to be post-menopausal. Female subjects who have a clinical history of sterility but do not have a screening FSH value cannot be classified. This subgroup will only be used for DXA and laboratory bone marker analyses.

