12.2. LABORATORY EVALUATIONS

Observed and change from baseline clinical laboratory data (hematology, biochemistry and continuous urinalysis parameters) will be summarized by visit using descriptive statistics.

Observed, change from baseline and percent change from baseline values for BSAP, parathyroid hormone, vitamin D and urine NTx will be summarized by visit using descriptive statistics. The summary will also be split by sex and baseline menopausal status (i.e., men, pre-menopausal women and post-menopausal women). For NTx only subjects who have a second void collected at the visit will be included in the summary presentations (including the plots specified below).

Urinalysis categorical data will also be summarized by visit. Descriptive statistics will be used for continuous data and counts and percentages for categorical data.

A shift table from baseline to visit, of normal, abnormal low, abnormal high and missing records will also be summarised for hematology, chemistry and urinalysis data, with marginal totals, using counts and percentages. If the reference range does not have a lower bound (e.g., reference range is 0 to x), the low columns/rows will be presented as ‘-’, rather than a count of zero.

Box plots of changes from baseline by visit and group will be presented for the clinical laboratory parameters hemoglobin, HbA1c, high density lipoprotein (HDL), low density

lipoprotein (LDL), lymphocytes, leukocytes, platelets, neutrophils, vitamin D, calcium, CK, ALT, AST, BSAP and urine N-terminal telopeptide (NTx) values. The whiskers will display the 5th and 95th percentiles. For the reporting group from the start of REN001-202 the box plot will be repeated for the overall mt-DNA-PMM versus nDNA-PMM groups and outliers (i.e., outside the 5th to 95th percentile) will be identified on the plot with subject ID. The number of observations contributing to each visit will be included on the plot. The box plot will be repeated for the parameters BSAP and urine N-terminal telopeptide (NTx) however these plots will be presented by sex and baseline menopausal status (i.e., men, pre-menopausal women and post-menopausal women).

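### The SAP's no-FSH default has no age limit, so amenorrhoeic women under 45 without a DXA scan fall into the post-menopausal bone-marker stratum

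*SAP*

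**What the plan says.** **Classification rule (SAP 8.5).**
- The main rule needs a hormone result: "Post-menopausal females have a screening FSH value ≥ 23.0 IU/L", together with either a last period more than a year before first dose or a confirmed history of sterility.
- A default covers women without a result. Those with a last period more than a year ago who "do not have a screening FSH value will also be assumed to be post-menopausal".
- A third sentence treats another group without a result differently: "Female subjects who have a clinical history of sterility but do not have a screening FSH value cannot be classified".
- None of the three sentences mentions age.

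**Where it is used.** SAP 8.5 says: "This subgroup will only be used for DXA and laboratory bone marker analyses". SAP 12.2 applies it to BSAP, parathyroid hormone, vitamin D and urine NTx: "The summary will also be split by sex and baseline menopausal status". Box plots of BSAP and NTx are repeated by the same strata. SAP 12 bases safety evaluations on each safety set, so the bone-marker split is not confined to scanned women.

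**The protocol's only definition (5.8.1).** "Post-menopausal, defined as 45 years or older and amenorrhoeic for at least 1 year PLUS have a serum follicle stimulating hormone (FSH) level" in the laboratory's post-menopausal range. It appears among the criteria for non-child-bearing potential. Protocol 8.6 names men, pre-menopausal women and post-menopausal women as DXA subgroups without defining them.

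**The concern.** The default treats a missing FSH as neutral and lets the date of the last period decide. That is reasonable if FSH is missing by accident in women of menopausal age. Here it is missing systematically in the women least likely to be menopausal, because the sampling schedule starts at 45.

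Protocol 1.4.2.6 names bone as a risk to be watched and commits the sponsor to monitoring turnover markers. The menopausal split is meant to make those tables interpretable. If younger amenorrhoeic women are counted as post-menopausal, that stratum mixes two kinds of women, and the pre-menopausal stratum may lose women who belong in it. The routine demography tables would not show this, because SAP 9.2 summarises menopausal status for the DXA scan set only.

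**Working it through.** The plan states no figure on this point, so there is none to reproduce. The check sets the sampling schedule beside the rule.

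**Step 1: who has a screening FSH?**
- Feeder study REN001-201 (SAP Appendix 2, footnote 9): women aged 45 or older, plus all women in the DXA sub-study.
- Option 1 (protocol 6.1.1): no FSH at entry unless a DXA scan is done and the woman was not confirmed post-menopausal in STRIDE.
- Option 2 (6.1.2) and Option 3 (6.1.3.1): from age 45, with the same DXA exception.
- Option 4 (6.1.4.1): from age 45, except that every woman having a DXA scan is tested.
- After baseline: Month 1 testing from age 45 (6.2), and testing at any age if menopausal symptoms develop. These are not screening values.

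So a woman under 45 without a DXA scan has no screening FSH by design. Such women are eligible: nDNA subjects enter from age 18 (protocol 4.1.1), and SAP 9.2 plans age bands of 18–25 and 26–45.

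**Step 2: apply both definitions, case by case.** All cases have a last period more than a year ago.

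| Case | Age | Screening FSH | SAP 8.5 | Protocol 5.8.1 |
|---|---|---|---|---|
| A | under 45 | none | post-menopausal | not post-menopausal (fails age and FSH) |
| B | under 45 | below 23.0 IU/L | not post-menopausal | not post-menopausal |
| C | under 45 | 23.0 IU/L or more | post-menopausal | not post-menopausal (fails age) |
| D | 45 or older | none | post-menopausal | not confirmed |
| E | any, with history of sterility | none | two sentences apply, with different answers | FSH condition not met |

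Case A is the problem. Comparing A with B shows why: two women with the same history and the same true FSH can get different labels only because one had a DXA scan and so had FSH drawn. Case C rests on hormone evidence and needs no age limit. Case E has no unique answer as written.

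**Step 3: size.** The documents give no sex mix, age mix, amenorrhoea rate or number of scans, so the share affected can only be illustrated. Let *a* be the percentage of all women who are misassigned and *p* the percentage truly post-menopausal. The misassigned share of the labelled stratum is *f* = *a*/(*a* + *p*). Every input below is an assumption, with half of women taken to be under 45:
- 2% of them amenorrhoeic, *p* = 40%: *a* = 0.5 × 2 = 1; *f* = 1/41 = 2.4%.
- 5% amenorrhoeic, *p* = 30%: *a* = 0.5 × 5 = 2.5; *f* = 2.5/32.5 = 7.7%.
- 15% amenorrhoeic, *p* = 20%: *a* = 0.5 × 15 = 7.5; *f* = 7.5/27.5 = 27.3%.

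All three count every amenorrhoeic woman under 45 as lacking FSH. Scanned women do have it, so on these inputs the figures are upper values.

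The stratum mean moves by *f* times the difference between the misassigned women and the truly post-menopausal women. An assumed *f* of 5% to 20% moves it by 0.05 to 0.20 of that difference.

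**The case against.** The case for leaving the rule alone is substantial. No hypothesis is tested (SAP 8.1), and SAP 8.5 uses subgroups only to explore consistency. The named bone endpoint is BMD by DXA, and FSH testing of scanned women largely covers those strata. The bone markers are also summarised unsplit, and those tables are unaffected. The split tables include change and percent change from each woman's own baseline, so mixing distorts changes only if the two kinds of women change differently, which nothing in the documents shows. The SAP is entitled to define its own strata, and the number affected may be very small.

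All of that stands, and it limits the consequence. It does not justify a rule that assigns a stratum with no supporting evidence, especially when the next sentence declines to do so for sterile women in the same position.

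A reader might go further in four ways that the documents do not support:
- **That the SAP breaches the protocol.** The age-45 definition serves the assessment of child-bearing potential, and protocol 8.6 leaves the analysis subgroups undefined.
- **That about a quarter of the stratum is contaminated.** The 27.3% above pairs the highest assumed amenorrhoea with the lowest assumed post-menopausal share. Equally unsourced inputs give 2.4%.
- **That the BMD strata are compromised.** The FSH requirements for scanned women largely close the gap there.
- **That women under 45 without FSH should simply be called pre-menopausal.** That would mislabel some sterile women, including any who have had a bilateral oophorectomy, which protocol 5.8.1 recognises as a separate ground for non-child-bearing potential.

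**Conclusion.** The point holds as a misspecified default. Read together, SAP 8.5 and the FSH schedule place any woman under 45 with no DXA scan and a last period more than a year ago in the post-menopausal stratum of the bone-marker summaries, on amenorrhoea alone. The overlap with the sterility sentence leaves a second group with two possible labels.

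The effect is confined to descriptive bone-marker tables and plots split by menopausal status. No test or error rate is involved. The number of women affected cannot be derived from the documents and may be small. The conclusion rests only on the wording of the rule and the sampling schedule. It needs no assumption about why younger women are amenorrhoeic or how many there are. It is worth correcting before database lock because the correction is cheap and the misassignment would not be visible in the planned demography tables.

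**What to change.** In SAP 8.5:
1. Add a condition of age 45 or older to the no-FSH default. Leave the FSH-based rule without an age limit.
2. Treat women under 45 with a last period more than a year ago and no FSH as unclassified, in line with the existing handling of sterile women without FSH.
3. State that unclassified takes precedence where the amenorrhoea and sterility sentences both apply.
4. Let a pre-dose FSH from the REN001-202 baseline count as well as a screening value. Option 2 draws FSH at its baseline visit and has no separate screening visit. Month 1 FSH should not be used: it is an on-treatment sample drawn mainly from age 45, and the split is by baseline status.
5. Footnote the split bone-marker tables with the number of unclassified women.

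The cost is a few lines of SAP text and one derivation, using data already collected and no added tests. The downside is that a few women drop out of the menopausal-status split; they remain in the overall bone-marker summaries.

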8.6. BASELINE DEFINITION

Subjects will have up to 2 baselines for endpoints:

- The last available non-missing assessment prior to study drug administration in REN001-201 (Day 1). This baseline will be used for analyses from the start of REN001-201 and, for those who receive mavodelpar in REN001-201, from the start of REN001 treatment analyses.
- The last available non-missing assessment prior to study drug administration in REN001-202. This baseline will be used for analyses from the start of REN001-202, and from the start of REN001 treatment for those subjects who:
 - received placebo in REN001-201
 - enter REN001-202 having exited REN001-201
 - enter REN001-202 having exited REN001-101
 - have nDNA-PMM

For those subjects who enter REN001-202 from REN001-201 at the REN001-201 W24 or FU visits the baseline should be from the assessments at those visits.

Questionnaires collected on the first day of dosing in either study will be considered as a baseline assessment within the context of the above definitions.

Note, to allow for scheduling of the eye examinations and DXA scans the REN001-201 Week 24 (Month 6) assessment can occur up to 14 days or 28 days respectively, after the visit. Hence, this assessment could occur after the start of administration of mavodelpar in REN001-202; this period is not considered sufficient time to have an impact on the results. Therefore, these assessments can still be considered a baseline record provided it occurs within 14 days for eye examinations or 28 days for DXA scans, of the first dose of mavodelpar.

9. ANALYSIS OF DISPOSITION, DEMOGRAPHIC AND BASELINE CHARACTERISTICS, AND MEDICATION

9.1. SUBJECT DISPOSITION AND WITHDRAWALS

To account for all pathways into REN001-202 a summary including REN001-201 and REN001-202 disposition will be generated. For REN001-201 the summary will be split by REN001-201 treatment groups and present the number (%) of subjects who were:

- Dosed in REN001-201 (% not required)
- Discontinued treatment in REN001-201 (along with reasons)
- Completed treatment in REN001-201 and did not enrol in REN001-202

Percentages will be based on the number of subjects dosed in REN001-201.

For REN001-202 the summary will be split by REN001-101 subjects, nDNA-PMM subjects, and the 6 REN001-201 enrolment pathway options:

1. REN001-201 REN001 enrolled at W24 visit
2. REN001-201 REN001 enrolled at FU visit
3. REN001-201 REN001 enrolled after exiting
4. REN001-201 Placebo enrolled at W24 visit
5. REN001-201 Placebo enrolled at FU visit
6. REN001-201 Placebo enrolled after exiting.

The summary will present the number (%) of subjects who were:

- Screened (for subjects who enrolled after exiting REN001-201, REN001-101 subjects or nDNA-PMM subjects)
- Rescreened (applicable for subjects who enrolled after exiting REN001-201, REN001-101 subjects or nDNA-PMM subjects)^a
- Not dosed in REN001-202^a
- Dosed in REN001-202^a
- Completed REN001-202^b
- Withdrew from REN001-202 (along with reasons)^b
- Ongoing in REN001-202 (applicable for interim analyses of REN001-202)^b
- In each analysis set (safety, FAS, PK and DXA)^b

^a Percentages will be based on the number of subjects in the REN001-202 screened set for subjects who enrolled after exiting REN001-201, REN001-101 subjects or nDNA-PMM subjects.

^b Percentages will be based on the number of subjects dosed in REN001-202.

The number (%) of subjects in the FAS and safety analysis sets will also be summarized from the start of REN001-201 and the number (%) in the safety analysis set from the start of REN001 treatment. The denominator will be based on the number of subjects dosed in REN001-201 and the number of subjects dosed with mavodelpar respectively.

For each scheduled visit the following number (%) of subjects will be presented for each safety analysis set:

- Who attended the visit
- Who missed the visit
- Who withdrew from the study prior to the visit

If a subject does not have a record for a visit and did not withdraw from the study, then the record will be counted as due to missing. For subjects who withdraw from the study then the date of study withdrawal will be used to assess whether the subject missed the visit. Any missing records prior to this date will be classed as missing and any missing records after this date will be classed as a withdrawal.

For interim reporting some subjects will still be ongoing in REN001-202 at the time of the data cut, so in addition to the above categories the number of subjects with the potential to reach a REN001-202 visit will be included; and therefore, the number who attended, missed or were withdrawn prior to visit will be based on those with the potential to reach the REN001-202 visit. Subjects will be assessed as to whether they have the potential to reach a REN001-202 visit using the duration from the first dose in REN001-202 to the date of the data cut. If the duration is greater than the target visit day, then the subject will be deemed to have the potential to reach the REN001-202 visit. If the subject attends a visit they will automatically be categorized as having the potential to reach the visit.

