7.2. SAFETY ANALYSIS SETS

There will be a separate safety set for each of the approaches for summarizing the data.

- from the start of REN001-202 – will include all REN001-202 subjects who signed the REN001-202 informed consent form, completed screening and received at least one dose of mavodelpar study medication in REN001-202.
- From the start of REN001-201 – will include all subjects who signed the REN001-201 informed consent form, completed screening and received at least one dose of study medication in REN001-201.
- from the start of REN001 treatment – will include all subjects who signed the informed consent form (REN001-201 form for mavodelpar REN001-201 subjects and REN001-202 form for REN001-201 placebo subjects), completed screening and received at least one dose of mavodelpar study medication in either REN001-201 (mavodelpar subjects in REN001-201) or REN001-202 (placebo subjects in REN001-201).

The ‘from the start of REN001-201’ safety analysis set summaries will be based on the actual treatment received. The safety analysis sets will be used for all baseline and safety analyses.

A listing safety analysis set will be used for listings. This will include all subjects who signed the informed consent form and received at least one dose of study medication in either REN001-201 or REN001-202.

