subjects represent. These 5 reporting groups are referenced in square brackets alongside the descriptions below. The summaries are:

- From the start of REN001-202 Summaries will be presented by mutation group (REN001 100 mg mtDNA-PMM [Groups 1 to 4] and REN001 100 mg nDNA-PMM [Group 5]). The mtDNA-PMM group will also be split by:
 - Placebo > REN001 100 mg [Group 1] – subjects who received placebo in REN001-201 and enrolled at REN001-201 W24, FU or after exit.
 - REN001 100 mg > REN001 100 mg [Group 2] – subjects who received mavodelpar in REN001-201 and enrolled at REN001-201 W24 visit.
 - REN001 100 mg >FU> REN001 100 mg [Group 3] – subjects who received mavodelpar in REN001-201 and enrolled at REN001-201 FU visit.
 - REN001 100 mg >Exit> REN001 100 mg [Groups 4a and 4b] – subjects who received mavodelpar in REN001-201 and enrolled after exiting REN001-201 or subjects who took part in REN001-101 study.

Summaries will extend out to Month 48, where applicable.

- From the start of REN001-201 which will be split by REN001-201 treatment group (REN001 100 mg [Groups 2, 3 and 4a] and placebo [Group 1]). Subjects who enrol in REN001-202 at REN001-201 Exit will only have their REN001-201 data included in these summaries. Baseline summary tables (disposition, demography, baseline characteristics, medical history and prior medications) will also include an overall summary.

Summaries will extend out to Month 54, where applicable, for all subjects who complete both studies.

- From the start of REN001 treatment [Groups 1, 2, 3 and 4]. Subjects who enrol in REN001-202 at REN001-201 Exit and receive mavodelpar in REN001-201 [Group 4a] will be counted as 2 separate subjects. Summaries will be presented over all subjects (REN001 100 mg).

Summaries will extend out to Month 54, where applicable, for subjects who receive mavodelpar in REN001-201 and enrol in REN001-202 at REN001-201 W24 or FU; for all other subjects summaries will extend to Month 48.

In addition, for summaries from the start of REN001 there is only Week 2 (Month 0.5), Week 18 (Month 4.5), Month 1 (Month 7) and Month 3 (Month 9) for subjects who receive mavodelpar in REN001-201 and therefore this visit will not be included in the by visit summaries. Refer to [Section 3.8](#) for diagram of visit assignment.

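### As written, the final by-visit disposition table from the start of REN001-201 counts non-withdrawn subjects who never entered REN001-202, and Exit subjects, as having missed every visit after Month 6

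*SAP*

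**What the plan says.** SAP Section 9.1 introduces the by-visit table with "For each scheduled visit the following number (%) of subjects will be presented for each safety analysis set". It then lists three outcomes: attended, missed, or withdrew before the visit.

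Two rules sort the subjects without a record. A subject who lacks a record and "did not withdraw from the study, then the record will be counted as due to missing". For a subject who did withdraw, the withdrawal date decides: "Any missing records prior to this date will be classed as missing and any missing records after this date will be classed as a withdrawal".

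At the interim only, the next paragraph of Section 9.1 bases the three counts on subjects with the potential to reach the REN001-202 visit. That potential is measured from the first REN001-202 dose to the data cut.

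Other parts of the SAP fix who is in the table:

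- Section 7.2, on the safety set that begins with REN001-201: it "will include all subjects who signed the REN001-201 informed consent form, completed screening and received at least one dose of study medication in REN001-201".
- Section 8.2: these summaries run to Month 54 where applicable, and "Subjects who enrol in REN001-202 at REN001-201 Exit will only have their REN001-201 data included in these summaries".
- Section 8.2: from the start of REN001 treatment, Group 4a subjects count as two separate subjects.
- Section 9.1, overall disposition: there is a row for subjects who "Completed treatment in REN001-201 and did not enrol in REN001-202", so the plan expects such subjects.

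**The concern.** A completer who never enters REN001-202 has no later record and has not withdrawn. An Exit subject may attend REN001-202 visits, but those visits are deliberately kept out of this presentation. Neither was due at a visit after Month 6 in this table, yet the three categories leave only missed for them.

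SAP Section 2 names informative missing data as a main limit on the long-term efficacy data. The by-visit table is where a reader would judge how much follow-up was lost and why. If subjects who were never due are pooled with subjects who were due and did not come, that judgement is blurred. Because this presentation is split by REN001-201 treatment group, unequal roll-over between the arms would also look like unequal visit attendance.

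**Working it through.** The plan states no figure to reproduce. The check applies the Section 9.1 rule literally to each type of subject, then sizes the effect under stated assumptions.

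**Classification at any visit after Month 6, start of REN001-201, final CSR**

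| Subject | Record in this presentation? | Withdrew from study? | Result |
|---|---|---|---|
| Rolled over at W24 or FU, attends | Yes | No | Attended |
| Withdrew from REN001-201 | No | Yes | Withdrew |
| Not withdrawn, never enrolled in REN001-202 | No | No | Missed |
| Exit subject | No (excluded, Section 8.2) | No | Missed |

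The third row can include more than treatment completers. Footnote 4 of SAP Appendix 2 recognises REN001-201 subjects who stop study drug without withdrawing from the study, and Protocol Section 4.1.1 requires completed STRIDE treatment for entry.

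**Start of REN001 treatment.** Mavodelpar subjects who never enrol are in this set and are classed the same way. For Group 4a, the first participation is missed at Month 12 while the second can be attended at Month 12, so one person can sit in both rows.

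**Interim.** A never-enrolled subject has no first REN001-202 dose, so cannot have the potential to reach a visit and drops out. An Exit subject has a first dose, so stays in and is still missed.

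**Size.** Let T be the continuing subjects who truly missed the visit, C the non-withdrawn subjects who never enrolled, E the Exit subjects and N the number dosed in REN001-201.

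- Missed, as written, final CSR = T + C + E
- Excess = C + E, or 100 × (C + E)/N percentage points

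The documents give none of C, E or N. SAP Section 3.5 gives only an estimate of about 150 mtDNA-PMM subjects entering REN001-202. The illustration assumes N = 100, 5 withdrawn in REN001-201, no later withdrawals, and a true missed rate of 5% among continuing subjects. Continuing = 100 − 5 − C − E, and T = 0.05 × continuing.

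| C | E | Continuing | T | Missed as written, final | Missed as written, interim |
|---|---|---|---|---|---|
| 5 | 1 | 89 | 4.45 | 4.45 + 6 = 10.45 | (4.45 + 1)/90 = 6.1% |
| 15 | 3 | 77 | 3.85 | 3.85 + 18 = 21.85 | (3.85 + 3)/80 = 8.6% |
| 30 | 5 | 60 | 3.00 | 3.00 + 35 = 38.00 | (3.00 + 5)/65 = 12.3% |

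The interim denominator is continuing plus Exit subjects, and assumes all of them have been dosed long enough to reach the visit. The true missed rate is 5.0% of continuing subjects in every row.

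**The case against.** The strongest reply is that the SAP is silent on these subjects, not wrong. Section 8.2 extends the summaries to Month 54 where applicable, for subjects who complete both studies. Section 3.8 treats an Exit subject's two participations as separate subjects. A never-enrolled subject arguably has no scheduled REN001-202 visit. The table shells are a separate document and may deal with this.

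This does not remove the point. The Section 8.2 sentence sets how far the summaries run. Read as a population rule, it would also drop everyone who withdrew during REN001-202, which defeats the withdrew row. Section 9.1 states a positive rule with three outcomes, and the final CSR text has no not-applicable outcome.

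Three parts of the reply do stand:

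- The interim rule already removes the never-enrolled, so for them the problem is confined to the final CSR.
- The overall disposition summary counts completers who did not enrol, and Exit subjects by arm. The excess is the same at every later visit, so a careful reader could largely subtract it. Subjects who stopped drug but stayed in REN001-201 are harder to isolate, because that summary counts treatment discontinuation and not study withdrawal.
- Section 10 does not cite the Section 9.1 rule. A reader might infer that the same misclassification runs through the efficacy tables and the PGIC and PGIS stacked bars. Those outputs do show withdrawn and missing subjects, but on the FAS, and the SAP does not say how the two are separated there. Carry-over is possible, not established.

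**Conclusion.** The point holds for the by-visit disposition table. In the final CSR, from the start of REN001-201 and from the start of REN001 treatment, the written rule overstates missed visits after Month 6. The excess is the number of non-withdrawn subjects who did not continue plus, from the start of REN001-201, Exit subjects or, from the start of REN001 treatment, the first participations of Group 4a. At the interim only the Exit part remains. The actual size is unknown; the figures above rest on assumed proportions and show only how the excess scales.

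Two stronger readings are tempting and are not supported. A reader might infer that every 10% of dosed subjects who do not roll over adds 10 points of false missed visits. It does not, because subjects who withdrew from REN001-201 also fail to roll over and are correctly classed as withdrawn. A reader might also infer that the long-term results are distorted. Means, changes from baseline, percentages based on non-missing values and AE incidence do not depend on this split, and no formal testing is planned. The consequence is a misleading description of follow-up, which is modest but cheap to prevent.

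**What to change.** In SAP Section 9.1, add a fourth category for visits after Month 6: did not continue into REN001-202 at W24/FU (not due). Place in it the non-withdrawn subjects who never enrolled, Exit subjects (start of REN001-201) and the first participation of Group 4a (start of REN001 treatment), and take them out of missed. Apply it at both interim and final, and in both sets.

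Keep all dosed subjects in the denominator. In the middle example the table would then read attended 73.15 (0.95 × 77), missed 3.85, withdrew 5 and did not continue 18, which sum to 100. Basing percentages only on W24/FU roll-overs might seem the natural next step. But SAP Section 2 says this presentation is meant to cover everyone randomized and dosed in REN001-201, and such a base would hide non-continuation, which may itself be informative.

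State in Section 10 whether the efficacy tables and the PGIC and PGIS bars use the same withdrawn/missing split. If they do, show the new category there too.

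The cost is a few sentences of SAP text and one extra row, or one bar segment. No new data are needed.
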